### **6.3 Analysis Populations**

#### **6.3.1 Full Analysis Set Population**

The Full Analysis Set Population includes all subjects who received at least one dose of study medication. Only subjects with clear documentation that no study medication was received may be excluded. The Full Analysis Set Population will be the primary population for the efficacy analyses. In the event of allocation errors, subjects will be analyzed for efficacy according to the treatment to which they were randomized.

#### **6.3.2 Modified Intent-to-Treat Analysis Population**

The Modified Intent-to-Treat (mITT) Population will consist of all patients who receive at least one dose of study medication, have a valid baseline and at least 1 post-baseline MRI or ALT assessment. In the event of allocation errors, subjects will be analyzed for efficacy according to the treatment to which they were randomized.

#### **6.3.3 Safety Population**

The Safety Population includes all subjects who received at least one dose of study medication. Only subjects with clear documentation that no study medication was received may be excluded. In the event of treatment allocation errors, subjects will be analyzed for safety according to the treatment group they received.

#### **6.3.4 Per Protocol Population**

The Per Protocol Population includes all subjects who complete 24 weeks of study treatment and have MRI and ALT measured at baseline and at week 24 and no major protocol violations, determined prior to break of the treatment blind.

### **6.3.5 PK Substudy Population**

The PK Substudy Population will consist of all patients who receive at least one dose of JKB-121, have no significant deviation in dosing that will affect PK evaluation, and have sufficient evaluable plasma PK concentrations to calculate PK parameters.

### **6.4 Subject Disposition**

Subject disposition information will be summarized by randomized treatment group and total. Number and percentage of subjects who are randomized, who are in each analysis population, who complete the study, and who withdraw early from the study will be presented. The primary reasons for early withdrawals will also be tabulated. The number of randomized patients within each treatment group will be used as the denominator for the percentage calculations.

### **6.5 Demographic and Baseline Characteristics**

Demographics and baseline characteristics will be summarized descriptively by treatment group and total for the Safety Population and mITT Population.

Demographic and baseline characteristics include, but are not limited to, age at informed consent, gender, race, ethnicity, body weight, body mass index (BMI), and baseline efficacy measures (percentage fat content of the liver measured by MRI, ALT, AST, GGT).

Randomization stratum (diabetic status) will also be summarized. Continuous variables will be summarized by descriptive statistics. Categorical variables will be summarized by the number and percentage of patients in corresponding categories. The baseline is defined in Section 6.2, Baseline, Endpoint, and Other Statistical Considerations.

### **6.6 Medical History**

Medical history will be coded using the Medical Dictionary for Regulatory Activities (MedDRA). The numbers and percentages of subjects in each treatment group and in total having medical/surgical history will be summarized by system organ class and preferred term for the Safety Population. All medical history will be listed.

Liver histology scoring (steatosis grade, ballooning, lobular inflammation, fibrosis stage, and NAS score) will be summarized with numbers and percentages of subjects in each treatment group.

### **6.7 Prior and Concomitant Medications**

Medication start and stop dates that are recorded on the Prior & Concomitant Medications case report form will be used to determine whether the medications are prior or concomitant to the study treatment. Concomitant medications are defined as those used on or after the first dose of study treatment. Prior medications are defined as those used prior to and stopped

before the first dose of study treatment. All prior and concomitant medication verbatim terms will be coded using the World Health Organization Drug Dictionary. The numbers and percentages of subjects taking concomitant medications in each treatment group and in total will be summarized by anatomic and therapeutic chemical term and preferred term for the Safety Population. All prior and concomitant medications will be listed.

## 6.8 Study Medication Exposure and Compliance

Subjects' exposure to randomized study medication will be summarized with descriptive statistics for the Safety Population.

Days of exposure is defined as:

$$\textit{date of last dose of study drug} - \textit{date of first dose} + 1$$

If a subject has been instructed to stop dosing for any portion of the study, for example due to AE, then the days of interruption will be subtracted from the days of exposure. The days of interruption is defined as:

$$\textit{last date of interruption} - \textit{first date of interruption} + 1$$

If the last dose of study drug is missing, the date of completion/early termination will be used. In addition, a contingency table will be provided to display the number and percentage of subjects in each treatment group with exposure in the following categories: 1-56 days (1-8 weeks), 57-112 days (8-16 weeks), 113-168 days (16-24 weeks), 169-196 days (24-28 weeks), and  $\geq 197$  days ( $> 28$  weeks).

Summary statistics will be presented for percent compliance to study medication by treatment group and total. The count and percentage of subjects will also be tabulated by groups with overall compliance  $< 80\%$ ,  $80\%$  to  $120\%$ , and  $> 120\%$ .

The percent compliance to study medication will be calculated as:

$$100 \times \frac{\textit{total number of tablets dispensed} - \textit{total number of tablets returned}}{\textit{days of exposure} \times 2 - \textit{days of interruption}}$$

If a subject has been instructed to take half dose (1 tablet per day) for any portion of the study, for example due to AE, then the percent compliance will be calculated as:

$$100 \times \frac{\text{total number of tablets dispensed} - \text{total number of tablets returned}}{\text{days of regular exposure} \times 2 + \text{days of half dose exposure} - \text{days of interruption}}$$

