12.4 Toxicity Management Guidelines

The toxicity management will be based on DAIDS AE Grading system,

Hepatic toxicity:

ALL patients will have increased liver enzymes at baseline. Liver function tests will be monitored with each visit. For any elevated ALT 5-10.0 X ULN (Grade 3 or 4) on study drug, repeat testing and evaluation will be performed in 1 week. Treatment will be interrupted for drug-related Grade 3 AE until their AE Grade is less than 3. Liver function tests and assessment will be performed weekly to ensure resolution of Grade 3 AE. Study drug may be resumed following confirmation of resolution of Grade 3 AE or if investigator confirms AE is keeping with patient's underlying NASH. The investigator must assess whether or not Grade 3 AE is clinically or not clinically significant in the setting of NASH and in reference to baseline ALT levels. Increases in liver enzymes $> 3 \times$ subject's baseline will prompt retesting and patient examination within 1 week. Increases in liver enzymes $> 5 \times$ subject's baseline will prompt immediate drug discontinuation and withdrawal from study. For non-drug related Grade 3 AE, Investigator will perform further clinical management based on subject's clinical condition and/or other biochemistry results.

DAIDS Grading	Lab Value						INR	Clinical management	
	ALT *		AST		Bilirubin (total)			Non Drug Related	Drug Related
Grade 1	1.25-2.5 x ULN	and/or	1.25-2.5 x ULN	and/or	1.1-1.5 x ULN	and/or	1.2-1.3	Non treatment modification	
Grade 2	2.6-5.0 x ULN	and/or	2.6-5.0 x ULN	and/or	1.6-2.5 x ULN	and/or	1.4-1.5	Non treatment modification	
Grade 3	5.1-10.0 x ULN	and/or	5.1-10.0 x ULN	and/or	2.6-5.0 X ULN	and/or	1.5-2.0	Further clinical management will be judged by Investigator	Treatment interruption may be suggested by Investigator
Grade 4	$> 10.0 \times$ ULN	and/or	$> 10.0 \times$ ULN	and/or	$> 5.0 \times$ ULN	and/or	> 2.0	Treatment termination and withdraw	

* Subjects with elevated ALT > 10.0 ULN will be withdrawn from this study.

Discontinuation of treatment should be considered if:

- ALT or AST $> 10 \times$ ULN
- ALT or AST $> 5 \times$ ULN for more than 2 weeks
- ALT or AST $> 3 \times$ ULN and total bilirubin $> 2 \times$ ULN or INR > 1.5
- ALT or AST $> 3 \times$ ULN with the appearance of fatigue, nausea, vomiting, right upper quadrant abdominal pain, fever, rash or eosinophilia ($> 5\%$).

Other toxicities

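### The SAP 6.8 compliance formula subtracts dosing interruptions at the wrong rate, so percent compliance is biased for interrupted subjects and some fall in the wrong band

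*SAP*

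**What the plan says.** SAP 6.8 (Study Medication Exposure and Compliance) builds percent compliance in three steps.

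- **Exposure.** Days of exposure run from first to last dose, both days counted. An adjustment follows: "If a subject has been instructed to stop dosing for any portion of the study", "then the days of interruption will be subtracted from the days of exposure". Days of interruption are counted the same way, from first to last interrupted date inclusive.
- **Full-dose compliance.** The numerator is tablets dispensed minus tablets returned. The denominator is 2 × days of exposure − days of interruption.
- **Half-dose compliance.** The denominator is 2 × regular-dose days + half-dose days − days of interruption.

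Summary statistics are given by treatment group and in total. In addition, "The count and percentage of subjects will also be tabulated by groups with overall compliance" below 80%, from 80% to 120%, and above 120%.

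SAP 4.2 gives the regimen as one tablet twice daily. Protocol 12.4 foresees interruptions; its hepatic toxicity text states: "Treatment will be interrupted for drug-related Grade 3 AE until their AE Grade is less than 3".

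**The concern.** A compliance denominator should equal the number of tablets the subject was due to take. Here interruption days appear twice: once in the adjustment to days of exposure and again as a separate term in the denominator. The second subtraction is also on a different scale, one tablet per day where the regimen is two.

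The SAP does not say whether days of exposure in the denominator is before or after the adjustment. Two programmers could therefore produce different tables from the same data, and for the full-dose formula both would be wrong for any interrupted subject.

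The error falls only on interrupted subjects. SAP 6.8 names adverse events as a reason for stopping, so these will tend to be subjects with toxicity, and their number can differ by arm. With about 20 subjects per arm, one misclassified subject moves a band by 1/20 = 5 percentage points. Safety is part of the primary objective and choosing a dose for later studies is a secondary one, so readers will look at compliance when they compare the two doses.

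**Working it through.** **Inputs**

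- Tablets due per dosing day: 2 (SAP 4.2).
- Tablets due per interrupted day: 0 (dosing is stopped, SAP 6.8).
- Planned treatment: 24 weeks = 168 days (SAP 4.1).
- Bands: <80%, 80–120%, >120% (SAP 6.8).
- Length and frequency of interruptions: not given in the documents, so a range is shown.

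The plan gives no worked compliance figure to reproduce.

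**Notation.** S is the span from first to last dose, I the days of interruption, and f the true fraction of due tablets taken.

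**Full-dose formula**

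- Tablets due: 2(S − I).
- Net reading (exposure = S − I): denominator 2(S − I) − I = 2S − 3I, so 3 tablets are removed per interrupted day.
- Gross reading (exposure = S): denominator 2S − I, so 1 tablet is removed per interrupted day.
- Check: with I = 0 all three equal 2S, and a full complier scores 100%.

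**Full complier (f = 1), S = 168**

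| I (days) | Tablets due | Net reading | Gross reading |
|---|---|---|---|
| 14 | 308 | 308/294 = 104.8% | 308/322 = 95.7% |
| 28 | 280 | 280/252 = 111.1% | 280/308 = 90.9% |
| 42 | 252 | 252/210 = 120.0% | 252/294 = 85.7% |
| 43 | 250 | 250/207 = 120.8% | 250/293 = 85.3% |
| 56 | 224 | 224/168 = 133.3% | 224/280 = 80.0% |
| 57 | 222 | 222/165 = 134.5% | 222/279 = 79.6% |
| 84 | 168 | 168/84 = 200.0% | 168/252 = 66.7% |
| 112 | 112 | denominator 0 | 112/224 = 50.0% |

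**Where a full complier changes band**

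- Net: 2(S − I) > 1.2(2S − 3I) gives I > S/4. For S = 168 that is I > 42, so 43 days or more.
- Gross: 2(S − I) < 0.8(2S − I) gives I > S/3. For S = 168 that is I > 56, so 57 days or more.
- The thresholds scale with the span. For S = 56 they are 15 days (82/67 = 122.4%) and 19 days (74/93 = 79.6%).

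**Subjects who are not full compliers, S = 168**

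- Net, f = 0.70, I = 42: 0.70 × 252/210 = 176.4/210 = 84.0%. This subject first reaches 80% at I = 34: 0.70 × 268/234 = 80.2%.
- Net, f = 0.75: reaches 80% at I = 19, where 0.75 × 298/279 = 80.1%.
- Gross, f = 1.25: drops to 120% or below at I = 13, where 1.25 × 310/323 = 119.97%. An over-taker then passes as adequate.

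**Half-dose formula.** Example: 112 regular days and 56 half-dose days, I = 28, every due tablet taken.

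- Interruption in the regular period: tablets due 2 × 84 + 56 = 224. Net 224/196 = 114.3%; gross 224/252 = 88.9%.
- Interruption in the half-dose period: tablets due 2 × 112 + 28 = 252. Net 252/224 = 112.5%; gross 252/252 = 100%.

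**The case against.** Several points on the other side deserve weight.

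- **The consequences belong to different readings.** Full compliers above 120%, and poor compliers passing as adequate, arise only on the net reading. Full compliers below 80% arise only on the gross reading. Only one will be programmed, and the net reading is the literal one. This stands, but neither reading rescues the full-dose formula.
- **The half-dose formula is not always wrong.** Read gross, it is correct when the interruption lies wholly within the half-dose period, because one tablet a day is then the right amount to remove. This stands as a narrow exception. It does not hold on the net reading or when the interruption falls in the regular-dose period.
- **Band changes for full compliers need long interruptions**, over a quarter or a third of the span. At 14 days the result (104.8% or 95.7%) is still mid-band. Protocol 10.4.7 and 12.4 also list liver-enzyme criteria for discontinuation, and permanent discontinuation moves the last-dose date without triggering the error. This limits how often a full complier changes band. The percentage is still biased for any interruption, and subjects near a cut-off move sooner.
- **How often interruptions occur is unclear.** The Protocol 12.4 sentence is about hepatic toxicity, the table beneath it leaves interruption to the investigator, and for other Grade 3 or higher drug-related toxicities the text speaks of discontinuation. So the number of affected subjects, and any imbalance by arm, cannot be estimated from the documents.
- **Materiality is modest.** Compliance is descriptive only. The primary ANCOVA uses the Full Analysis Set, the Per Protocol definition in SAP 6.3.4 names no compliance threshold, and the days-of-exposure table does not use this denominator. All of this is accepted; it limits the importance of the error but does not remove it.

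**Conclusion.** The concern holds. Followed exactly, the full-dose formula gives the wrong number of expected tablets whenever there is an interruption: 3 tablets removed per interrupted day on the literal net reading, or 1 on the gross reading, where 2 is right. No other part of either document corrects it. The zero denominator at 112 interrupted days of 168 on the net reading shows that the formula is mis-specified rather than merely approximate.

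For a 28-day interruption the bias in a full complier is about +11 or −9 percentage points. Band errors depend on the length of the interruption, the span and true compliance, as shown in the working. These figures assume two tablets due per dosing day, none on interrupted days, and a 168-day span unless stated.

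The error is confined to the percent-compliance summary and its bands. It would reach the Per Protocol set only if compliance were used to define a major violation. That is an assumption: Protocol 13.4.4 leaves the definition of significant violations to the SAP, and the SAP lists none. The correction should be made, but the primary result does not depend on it.

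**What to change.** In SAP 6.8:

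1. State once that days of exposure are net of interruption days, and use that definition throughout.
2. Full-dose denominator: 2 × net days of exposure. Delete the trailing subtraction of interruption days.
3. Half-dose denominator: 2 × net regular-dose days + 1 × net half-dose days, each net of the interruption days that fall within it. Delete the trailing subtraction here too.

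A full complier then scores 2(S − I)/2(S − I) = 100% for every interruption length short of the whole span, and a 70% complier scores 70%. The half-dose version requires interruption dates to be assigned to the regular or half-dose period.

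The cost is two formula edits and one clarifying sentence, plus matching changes to the compliance program if it has been written. No dose, visit or clinical rule changes.

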	
• HbA1c and the homeostatic model assessment of insulin resistance (HOMA-IR)• Serum lipid profile: total cholesterol, triglycerides, low density lipoprotein (LDL) and high density lipoprotein (HDL) fractions. 
Liver Function:
 
• Mean change from baseline in serum ALT at week 24.• Mean serum aspartate aminotransferase (AST), alanine aminotransferase (ALT), and gamma-glutamyl transpeptidase (GGT) at weeks 4, 8, 12, 16, 20, and 24.• Proportion of subjects whose ALT level at week 24 is within normal range defined as < 20 U/L for women and < 30 U/L for men.
Exploratory Outcome Measures:	
• Mean serum concentrations of lipopolysaccharide (LPS), c-reactive protein (CRP), cytokeratin (CK)-18 fragments, proinsulin c-peptide, glucagon-like polypeptide (GLP-1) and adiponectin.• Relative levels of inflammatory cytokines, interferon gamma (IFN-γ), and tumor necrosis factor alpha (TNF-α)• Relative levels of regulatory T cells in the peripheral blood mononuclear cells (PBMC) samples including CD4, CD8, CD 25, Fox P3, NKT, and CD62 T cells.
Methodology:	
Study design	Randomized double blind, placebo control 3-arm parallel group, multi-dose single center study
Study duration	Up to 28 days for screening, 24 weeks of treatment and 28 days of follow-up. Subjects terminating study drug will be followed-up post-treatment for 28 days.
Number of Subjects:	The study will aim to recruit 60 subjects, randomized 1:1:1
Stratification:	Treatment allocation will be stratified by known diagnosis of diabetes status. Nondiabetic status will be defined as HbA1c \leq 6.0 and absence of any medications to treat diabetes. Diabetic status will be defined as HbA1c $>$ 6.0 and/or requiring medication for treatment of diabetes mellitus.
Study Drug:	JKB-121 oral tablet
Control Group	Placebo to match
Dose Regimens	Arm A: 5 mg JKB-121 twice daily. Arm B: 10 mg JKB-121 twice daily Arm C: Matching placebo twice daily All treatment dose regimens are administered per orally
Administration: Schedule:	Twice daily for 24 weeks

Study Population:	Adults with biopsy-proven nonalcoholic steatohepatitis (NASH)

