6.1 Duration of the Study

Subjects will be on treatment for up to 24 weeks. Subjects who experience adverse reaction will discontinue study drug but will continue to complete all protocol-specified follow-up visits, assessments and evaluations. They will then continue to be followed up for the remaining duration of the study. Unless otherwise recommended by the Independent Data Review Board (IDRB) or regulatory authorities, the study will continue until it accrues a minimum of 60 subjects complete the study.

Until formal conclusion of the study, subjects, investigators and all site study personnel will be remain blinded as to treatment allocation, except in the event of a medical emergency which necessitates unblinding.

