10.4.4 End of Treatment Visit 8 (week 24 ± 4 days)

Subjects must be in a fasted state for at least 8 hours prior to sample collection at these visits, which is a requirement for some of the blood tests that will be performed as noted below. If a subject has discontinued treatment, every attempt should be made to have the subject return to the site and complete the procedures / assessments that are required at the End of Treatment Visit (Week 24) and the Follow-up Visit (Week 28). The following will be performed for all subjects who meet the inclusion criteria and not of the exclusion criteria

- Verify the study drug was administered correctly
- Document drug accountability and any problems with drug administration in the source documents.
- Record vital signs
- Physical examination
- Record weight
- Electrocardiogram
- Urinalysis
- Hospital Anxiety and Depression Scale and Columbia Suicide Severity Scale
- Complete blood samples for:
 1. Complete blood count with differential
 2. Blood chemistry including: ALT, AST, albumin, alkaline phosphatase, bicarbonate, BUN, calcium, chloride, creatinine, glucose, LDH, magnesium, phosphorus, potassium, sodium, total and direct bilirubin, protein, uric acid, and GGT/
 3. Fasting glucose and insulin level for HOMA-IR
 4. Lipid panel
 5. Glycosylated hemoglobin
 6. Urine pregnancy test (only for women of childbearing potential).
 7. Serum and plasma samples for non-invasive biomarkers related to liver injury pathophysiology and/or TLR-4 pathway
 8. ELF test—Subjects must be in a fasted state prior to the sample collection
 9. FibroSURE/ FibroMAX/ FibroTest—Subject must be in a fasted state prior to the sample collection
 10. Additional blood sample needs to be collected for pharmacokinetic study
- Counsel subjects on weight loss, diet and exercise
- MRI for quantification of hepatic fat
- Record any adverse events occurring after signing of the informed consent form
- Record all medications that the subject has taken since prior visit

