10.4.5 Follow-up Visit 9 (week 28 ± 4 days) and Exit Interview

Subjects must be in a fasted state for at least 8 hours prior to sample collection at these visits, which is a requirement for some of the blood tests that will be performed as noted below. If a subject has discontinued treatment, every attempt should be made to have the subject return to the site and complete the procedures / assessments that are required at the End of Treatment Visit (Week 24) and the Follow-up Visit (Week 28). The following will be performed for all subjects who meet the inclusion criteria and not of the exclusion criteria

- Verify the study drug was administered correctly
- Document drug accountability and any problems with drug administration in the source documents.
- Record vital signs
- Physical examination
- Record weight

- Complete blood samples for:
 1. Complete blood count with differential
 2. Blood chemistry including: ALT, AST, albumin, alkaline phosphatase, bicarbonate, BUN, calcium, chloride, creatinine, glucose, LDH, magnesium, phosphorus, potassium, sodium, total and direct bilirubin, protein, uric acid, and GGT.
 3. Fasting glucose and insulin level for HOMA-IR
 4. Lipid panel
 5. Glycosylated hemoglobin
 6. Urinalysis
 7. Urine pregnancy test (only for women of childbearing potential).
 8. Serum and plasma samples for non-invasive biomarkers related to liver injury pathophysiology and/or TLR-4 pathway
 9. ELF test—Subjects must be in a fasted state prior to the sample collection
 10. FibroSURE/ FibroMAX/ FibroTest—Subject must be in a fasted state prior to the sample collection
- Counsel subjects on weight loss, diet and exercise
- Record any adverse events occurring after signing of the informed consent formRecord all medications that the subject has taken since prior visit

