10.4.6 Assessments for Early Discontinuation from Study

- Subjects discontinuing early should have an End of Treatment Visit performed, if possible and then have a Follow-up Visit 4 weeks later

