## 4 STUDY OVERVIEW

### 4.1 Study Design

[figure not shown]
This is a randomized, double-blind, placebo controlled, parallel-group, phase II trial of JKB-121 in treating subjects with biopsy-proven NASH.

Subjects will be randomized at study entry to placebo twice daily, 5 mg twice daily, or 10 mg twice daily of JKB-121 orally to improve NASH with regard to biochemical and MRI/MRS features of NASH in a 1:1:1 ratio.

- Treatment Group 1: placebo twice a day orally
- Treatment Group 2: 5mg of JKB-121 twice a day orally
- Treatment Group 3: 10 mg of JKB-121 twice a day orally

The maximum time on study drug for each subject is 24 weeks with an additional 4 weeks of follow-up.

This allocation is shown diagrammatically below:

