### **6.11.1 Adverse Events**

For the purposes of this study, any sign (including a clinically significant laboratory result) or medical diagnosis noted by medical personnel, or symptom reported by the subject, regardless of relationship to investigational drug, that is treatment-emergent is considered to be an AE. All adverse events reported by the subject or observed by study site personnel from time of informed consent until completion of the study or premature withdrawal must

be recorded in the subject's CRF as per the CRF instructions. All AEs will be coded using Medical Dictionary for Regulatory Activities (MedDRA).

Treatment-emergent adverse events (TEAEs) are defined as those AEs that have a start date on or after the first dose of study medication, or occur prior to the first dose and worsen in severity or relationship to study medication after the first dose. AEs beginning >7 days after last dose will not be considered treatment emergent. An overview of AEs will be provided by treatment group and in total for the following information:

- All TEAEs,
- Maximum severity of TEAEs,
- Study drug-related TEAEs,
- Maximum severity of drug-related TEAEs,
- All serious adverse events (SAEs),
- All treatment-emergent SAEs,
- Drug-related SAEs,
- Death due to AEs,
- Withdrawals due to AEs, and
- Withdrawals due to study drug-related AEs.

The numbers and percentages of subjects with TEAEs will be summarized for each treatment group and in total by MedDRA system organ class and preferred term. Similar summaries will be provided by maximum severity. Drug-related TEAEs will be summarized in the same manner. Listings of SAEs and AEs leading to study medication discontinuation will be provided.

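### The substitute for a missing last-dose date is undefined and not capped at the end of dosing, so off-drug days can be counted as exposure and reported compliance lowered

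*SAP*

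**What the plan says.** SAP section 6.8 defines days of exposure as last-dose date minus first-dose date plus 1, with days of instructed interruption subtracted. It then adds: "If the last dose of study drug is missing, the date of completion/early termination will be used". The substituted date is not defined further. Exposure also enters the compliance denominator (twice the days of exposure, less days of interruption). The numerator is tablets dispensed minus tablets returned. Compliance is tabulated as below 80%, 80% to 120%, and above 120%. Exposure is tabulated in bands that include 169-196 days and 197 days or more.

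SAP section 4.1 fixes the dosing period: "The maximum time on study drug for each subject is 24 weeks with an additional 4 weeks of follow-up". The protocol synopsis gives the same structure in days: "24 weeks of treatment and 28 days of follow-up". The last visit is Protocol section 10.4.5, "Follow-up Visit 9 (week 28 ± 4 days) and Exit Interview".

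For early stoppers, Protocol section 6.1 covers subjects who stop drug for an adverse reaction: "They will then continue to be followed up for the remaining duration of the study". Protocol section 10.4.6 says: "Subjects discontinuing early should have an End of Treatment Visit performed, if possible and then have a Follow-up Visit 4 weeks later".

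SAP section 6.11.1 uses the last dose for a different purpose: "AEs beginning >7 days after last dose will not be considered treatment emergent".

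**The concern.** A completer finishes dosing at Week 24 and finishes the study at Week 28. If the completion date stands in for the last dose, four weeks without drug are counted as treatment. Someone who stops drug early but keeps attending could be credited with months of treatment that did not happen. Because the same exposure figure is in the compliance denominator, the error also pushes reported compliance down, and it can move a subject from the 80% to 120% row into the below-80% row.

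Safety is part of the primary objective and the arms have about 20 subjects each. One misplaced subject moves a row of the compliance table by 1/20 = 5 percentage points.

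**Working it through.** The documents give no exposure or compliance result, so there is no stated figure to reproduce. The check applies the SAP 6.8 formulas directly.

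**Which date is meant?**

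- SAP section 6.4 speaks of completing the study and of withdrawing early from it, not of completing treatment.
- Protocol section 13.4.2 separates completing the treatment programme from completing the study.
- SAP section 6.9.2.1 treats Week 28 as outside the treatment period.
- Against this, Protocol section 6.3.1 labels Visit 8 as end-of-study, and Protocol section 10.8 places the end-of-treatment visit at the time of withdrawal.

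Week 28 is therefore the natural reading for completers, but it is an inference.

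**Inputs.** Week 24 = 24 × 7 = Day 168 (window ±4: Days 164 to 172). Week 28 = 28 × 7 = Day 196 (window ±4: Days 192 to 200). Two tablets a day, no interruption, first dose on Day 1.

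**Completer, nominal days.**

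- Exposure: 196 instead of 168 days, a gain of 28 days; 196/168 = 1.167.
- Full compliance: 336 tablets / (2 × 196) = 336/392 = 85.7%, instead of 336/336 = 100%.
- In general, reported compliance = true compliance × 168/196. So 90% becomes 77.1%, 85% becomes 72.9% and 80% becomes 68.6%.
- True compliance that is reported as exactly 80%: 80 × 196/168 = 93.3%.

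**Completer, across the visit windows.**

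- Smallest gap: 192 − 172 = 20 days; full compliance shows as 172/192 = 89.6%.
- Largest gap: 200 − 164 = 36 days; full compliance shows as 164/200 = 82.0%.
- If completion meant Visit 8 instead, the gap would be about 0 to 1 day (167/168 = 99.4%).

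**Fully compliant subject who stops on Day d, stop not recorded as an interruption.**

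| Stop day | Follow-up visit 28 days later: compliance | Stays to Day 196: added days | Stays to Day 196: compliance |
|---|---|---|---|
| 56 | 112/168 = 66.7% | 140 | 112/392 = 28.6% |
| 84 | 168/224 = 75.0% | 112 | 168/392 = 42.9% |
| 112 | 224/280 = 80.0% | 84 | 224/392 = 57.1% |
| 140 | 280/336 = 83.3% | 56 | 280/392 = 71.4% |

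Such a subject falls below 80% if d/(d + 28) < 0.8, that is d < 112, in the first case. In the second case the condition is d/196 < 0.8, that is d < 156.8. In an arm of 20, one Day-56 stopper who stays to Day 196 adds 140/20 = 7 days to mean exposure.

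**Treatment-emergent window, only if the imputed date is carried over.** The nominal cut-off for a completer would move from 168 + 7 = Day 175 to 196 + 7 = Day 203.

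**The case against.** The strongest reply is that the SAP leaves a term undefined and does not plainly choose Week 28. Protocol section 6.3.1 supports a Visit 8 reading, and a termination dated at the withdrawal visit adds almost nothing. That stands as a limit on certainty. It does not rescue the rule, because neither place caps the substituted date. The exposure bands beyond 168 days fit the Week 28 reading: apart from overrun to about Day 172, this substitution is the main way to fill them. They do not prove it.

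Several stronger readings are tempting, and the documents do not support them:

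- **That 28 days is a minimum.** It is the nominal value for a completer. The windows give 20 to 36 days, and some terminations give near zero.
- **That fully compliant completers drop below 80%.** They show 82.0% to 89.6%. Those who cross the line are completers with true compliance of 80% or more but, nominally, under 93.3%, and some early stoppers.
- **That every early stopper is heavily overstated.** SAP 6.8 subtracts instructed interruptions. If the off-drug time is recorded that way, exposure comes back to about the true figure. A subject who still attends, with tablet counts and diaries reviewed, is also less likely to lack a last-dose date.
- **That compliance is always understated.** For a lost subject, unreturned tablets count as taken, which raises the numerator. The net direction is undetermined.
- **That adverse events are relabelled.** The substitution rule stands only in section 6.8. Section 6.11.1 does not say that the imputed date applies. Protocol section 12.1.2 also puts no end limit on treatment emergence.
- **That missing dates cluster in early stoppers or lost subjects.** This is plausible but not documented.

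**Conclusion.** The rule should be changed, as a minor point. On the natural reading, and only for subjects whose last-dose date is missing, a completer's exposure is overstated by nominally 28 days (+16.7%) and reported compliance is multiplied by about 0.857. For early stoppers the error ranges from near zero to well over 100 days, depending on how long they stay in follow-up and whether the off-drug time is recorded as an interruption. For completers the direction of the exposure error is known.

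The result assumes that completion means the Week 28 visit, twice-daily dosing from Day 1, no interruption, and reliable tablet returns. The number of affected subjects cannot be estimated from the documents. The effect is on descriptive exposure and compliance tables. The per-protocol definition names no compliance threshold, and no efficacy analysis uses exposure. Treatment-emergent classification is affected only if the same imputed date is used for the 7-day cut-off, which the SAP leaves open.

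**What to change.** Replace the sentence in SAP 6.8 with an ordered rule:

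1. If the last-dose date is missing, use the latest diary or drug-return evidence of dosing.
2. Failing that, use the earliest of the recorded treatment-stop date, the End of Treatment (Visit 8) date and the early-termination date.
3. Never use a date after the End of Treatment visit.

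State in SAP 6.11.1 whether the same imputed date governs the treatment-emergent window. Flag imputed cases in the listings and give their number by arm. A lost subject with only a termination date would still be uncertain, and the flag makes that visible.

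The cost is a few sentences and a little extra programming. Protocol section 9.5 already provides for diaries and tablet counts, so no new data are needed.
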